20.4 Data Collection

Data will be collected at the study sites either on source documents, which will be entered at the site into eCRFs, or through direct electronic data capture. The eCRFs will be supplied by the DSC. eCRFs are to be completed on an ongoing basis during the study. The medical chart and the source documents are the source of verification of data. Paper CRFs and eCRFs should be completed according to the CRF instruction manual and relevant instructions in the study operations manual. The investigator is responsible for maintaining accurate, complete and up- to-date records, and for ensuring the completion of the eCRFs for each research participant.

20.5 Data Acquisition and Entry

Completed forms and electronic data will be entered into the Advantage eClinical system in accordance with the Advantage eClinical User's Guide. Only authorized individuals shall have access to eCRFs.

20.6 Data Editing

Completed data will be entered into Advantage eClinical. If incomplete or inaccurate data are found, a query will be generated to the sites for a response. Site staff will resolve data inconsistencies and errors and enter all corrections and changes into Advantage eClinical.

20.7 Database Lock and Transfer

Data will be transmitted by the DSC to the NIDA central data repository as requested by NIDA. The DSC will conduct final data quality assurance checks and “lock” the study database from further modification. The final analysis dataset will be returned to NIDA, as requested, for storage and archive.

20.8 Data Training

The training plan for site staff includes provisions for training on assessments, eCRF completion guidelines, data management procedures, and the use of Advantage eClinical.

20.9 Data QA

To address the issue of data entry quality, the DSC will follow a standard data monitoring plan. An acceptable quality level prior to study lock or closeout will be established as a part of the data management plan. Data quality summaries will be made available during the course of the protocol.

23.0 APPENDIX A - Adverse Event Reporting Definitions and Procedures

Each participating site's principal investigator is responsible for study oversight, including ensuring human research subject protection by designating appropriately qualified and trained study personnel to assess, report, and monitor adverse events.

23.1 Definition of Adverse Events and Serious Adverse Events

An **Adverse Event** (AE) is any untoward medical occurrence in humans, whether or not considered study drug/intervention related which occurs during the conduct of a clinical trial. Any change from baseline in clinical status or any findings from lab results, x-rays, physical examinations, etc., that are considered clinically significant by the study medical clinician are considered AEs.

Suspected adverse reaction is any adverse event for which there is a reasonable possibility that the study drug/intervention caused the adverse event. A reasonable possibility implies that there is evidence that the study drug/intervention caused the event.

Adverse reaction is any adverse event caused by the study drug/intervention.

An **adverse event, suspected adverse reaction, or adverse reaction** is considered “**serious**” (i.e., a serious adverse event, serious suspected adverse reaction or serious adverse reaction) if, in the view of either the study medical clinician or sponsor, it:

- 1) Results in death: A death occurring during the study or which comes to the attention of the study staff during the protocol-defined follow-up period, whether or not considered caused by the study drug/intervention, must be reported.
- 2) Is life-threatening: Life-threatening means that the study participant was, in the opinion of the medical clinician or sponsor, at immediate risk of death from the reaction as it occurred and required immediate intervention.
- 3) Requires inpatient hospitalization or prolongation of existing hospitalization.
- 4) Results in persistent or significant incapacity or substantial disruption of the ability to conduct normal life functions. Is a congenital abnormality or birth defect.
- 5) Important medical event that may not result in one of the above outcomes, but may jeopardize the health of the study participant or require medical or surgical intervention to prevent one of the outcomes listed in the above definition of serious event.

23.1.1 Definition of Expectedness

Any adverse event is considered “unexpected” if it is not listed in the investigator brochure or the package insert or is not listed at the specificity or severity that has been observed. If neither is available then the protocol and consent are used to determine an unexpected adverse event.

23.2 Pregnancy

Any pregnancies that occur while a participant is enrolled in the study will be captured on a pregnancy CRF and not separately reported as an AE or SAE. Women who become pregnant

during the active treatment period will be discontinued from further medication administration, referred for medical care, and the pregnancy followed until an outcome is known.

23.3 Medical and Psychiatric History

A thorough medical and psychiatric history during the screening phase should record any chronic, acute, or intermittent preexisting or current illnesses, diseases, symptoms, or laboratory signs of the participant, to avoid reporting pre-existing conditions as new AEs and to assist in the assessment of worsening in intensity or severity of these conditions that would indicate an AE. Stable chronic pre-existing conditions, such as arthritis, which are present prior to clinical trial entry, are not considered to be AEs unless the medical clinician deems that the condition has worsened in intensity and/or frequency during the course of the study.

23.4 Site's Role in Eliciting and Reporting Adverse Events

Appropriately qualified and trained study staff will elicit participant reporting of AEs and SAEs at each study visit designated to collect AEs. Adverse events (medical and/or psychiatric) assessment will initiate with participant consent and follow-up will continue through 30 days post last study visit. Study staff will obtain as much information as possible about the reported AE/SAE to complete the AE/SAE forms and will consult with the lead team as warranted.

Standard reporting, within 7 days of the site becoming aware of the event, is required for reportable AEs. Expedited reporting (within 24 hours of their occurrence and/or site's knowledge of the event) is required for reportable SAEs (including death and life-threatening events). Local sites are responsible for reporting SAEs to their IRB, per their IRB's guidelines when operating under an IRB Authorization Agreement.

Site staff is required to enter reportable AEs and SAEs in the Advantage eClinical system. The AE form is used to capture reportable AEs (as defined in the protocol). Additional information may need to be gathered to evaluate serious adverse events and to complete the appropriate CRFs and the summary. This process may include obtaining hospital discharge reports, medical records, autopsy records or any other type of records or information necessary to provide a complete and clear picture of the SAE as well as events preceding and following the SAE. If the SAE is not resolved or stable at the time of the initial report or if new information becomes available after the initial report, follow-up information must be submitted as soon as possible.

Reportable adverse events will be followed until resolution, stabilization or study end. Any serious adverse reactions will be followed until resolution or stabilization even beyond the end of the study.

23.5 Site's Role in Assessing Severity and Causality of Adverse Events

Appropriately qualified and trained medical personnel will conduct an initial assessment of seriousness, severity, and causality when eliciting participant reporting of adverse events. A study medical clinician will review reportable AEs for seriousness, severity, and causality at least on a weekly basis.

23.6 Guidelines for Assessing Severity

The severity of an adverse event refers to the intensity of the event.

Grade 1	Mild	Transient or mild discomfort (< 48 hours), no or minimal medical intervention/therapy required, hospitalization not necessary (non-prescription or single-use prescription therapy may be employed to relieve symptoms, e.g., aspirin for simple headache, acetaminophen for post-surgical pain).
Grade 2	Moderate	Mild to moderate limitation in activity, some assistance may be needed; no or minimal intervention/therapy required, hospitalization possible.
Grade 3	Severe	Marked limitation in activity, some assistance usually required; medical intervention/ therapy required, hospitalization possible.

23.6.1 Guidelines for Determining Causality

The study medical clinician will use the following question when assessing causality of an adverse event to study drug/intervention where an affirmative answer designates the event as a suspected adverse reaction: Is there a reasonable possibility that the study drug/intervention caused the event?

Please note that for the purposes of this protocol, events assessed to be mild (Grade 1) and unrelated, though reportable on the manual adverse event tracking log, are not reportable in the electronic data capture system.

23.6.2 Site's Role in Monitoring Adverse Events

Local quality assurance monitors (Node QA staff) will visit study sites and review respective study data on a regular basis and will promptly advise sites to report any previously unreported safety issues and ensure that the reportable safety-related events are being followed to resolution and reported appropriately. Staff education, re-training or appropriate corrective action plan may be implemented at the participating site when unreported or unidentified reportable AEs or serious events are discovered, to ensure future identification and timely reporting by the site.

23.6.3 Sponsor's Role in Safety Management Procedures of AEs/SAEs

A NIDA-assigned Medical Monitor/Safety Monitor is responsible for reviewing all serious adverse event reports. All reported SAEs will generate an e-mail notification to the Medical Monitor, Lead Investigator, and designees. All SAEs will be reviewed by the Medical Monitor/Safety Monitor in Advantage eClinical and, if needed, additional information will be requested. The Medical Monitor will also report events to the sponsor and the Data and Safety Monitoring Board (DSMB). The DSMB will receive summary reports of all adverse events annually, at a minimum. The DSMB or the NIDA-assigned Medical Monitor may also request additional and updated information. Details regarding specific adverse events, their treatment and resolution, will be summarized by the Medical Monitor/Safety Monitor in writing for review by the sponsor and DSMB.

23.7 Regulatory Reporting for an IND study

Not applicable as this study is not being conducted under an IND application.

[figure not shown]
23.8 Reporting to the Data and Safety Monitoring Board

The DSMB will receive a listing of AEs and summary reports of all SAEs at a frequency requested by the DSMB, but at least annually. Furthermore, the DSMB will be informed of expedited reports of SAEs.

23.9 Participant Withdrawal

The study medical clinician must apply his/her clinical judgment to determine whether or not an adverse event is of sufficient severity to require that the participant is withdrawn from further study medication administration. Extended-release naltrexone will be discontinued in participants with evidence of clinically significant deterioration in hepatic function and/or acute hepatitis, as assessed by the study clinician. The study medical clinician should consult with the site principal investigator, the lead investigator and/or Medical Monitor as needed. If necessary, a study medical clinician may suspend any trial treatments and institute the necessary medical therapy to protect a participant from any immediate danger. A participant may also voluntarily withdraw from treatment due to what he/she perceives as an intolerable adverse event or for any other reason. If voluntary withdrawal is requested, or the participant has been removed from the study, the participant will be asked to complete an end of study visit to assure safety and to document end of treatment outcomes and will be given recommendations for medical care and/or referrals to treatment, as necessary.

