9.6 Participant Discontinuation

All participants will be followed for the duration of the study (25-28 weeks, depending on length of time required for completion of screening and enrollment procedures) unless they withdraw consent, or the investigator or sponsor decides to discontinue their enrollment. Reasons for the investigator or sponsor terminating a participant from the study may include, but are not limited to, the participant becoming a threat to self or others, lack of funding, or DSMB early termination of the study for safety or effectiveness reasons.

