13.5 Clinical Laboratory Tests

Trained staff will be responsible for collecting and processing biologic specimens. Local laboratories at participating sites will be used to conduct all laboratory tests with the exception of the PBMCs. Laboratories must participate in the Clinical Laboratory Improvement Act of 1998 (CLIA) or be accredited by the College of American Pathologists (CAP). If neither CLIA nor CAP is available, equivalent evidence of laboratory certification may be acceptable and must be discussed on a case-by-case basis with the Lead Team. Laboratories should provide reference ranges and proof of laboratory certification.

HIV-1 RNA PCR: will be drawn at screening, 12, and 24 weeks (or the end of study visit, if not week 24) for outcomes assessment. At screening, results of laboratory tests conducted within 90 days prior to date of informed consent will be acceptable.

CD4 Count (T-helper cells): will be drawn at randomization and at 12 and 24 week visits or the end of study visit, if not week 24, for secondary outcomes assessment. At randomization, results of laboratory tests conducted within 90 days prior to date of informed consent will be acceptable.

Peripheral Blood Mononuclear Cells (PBMCs): For all randomized participants (both TAU and XR-NTX), we will collect four 8mL or eight 4mL CPT tubes for PBMC analysis at randomization,

12, and 24 (or end of study visit if not week 24). Blood draws may coincide with other research blood draws. PBMC analysis will be conducted in a related NIH application to assess the effects of opioid blockade on TLR mediated immune responses at a later time. PBMC samples will be shipped to a lab at Oregon Health & Science University and kept indefinitely. PBMC samples will be used for immunologic testing. It is also possible that banked PBMC specimens will be shared with other investigators for performance of genetic testing in the future.

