24.2.5.3 Human Subject Protection

The study medical clinician will evaluate all pertinent screening and baseline assessments prior to participant randomization to ensure that the participant is eligible and safe to enter the study. Adverse events (AEs) and concomitant medications will be assessed and documented at each clinic visit. Individuals who experience an AE that compromises safe participation will be discontinued from further medication administration and provided referrals for other treatment or to specialized care. Study personnel will request that the participant complete an end of study visit to assure safety and to document end of treatment outcomes.

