24.2.5.4 Pregnancy

Pregnancy is an exclusion criterion for study participation. A positive pregnancy test post-randomization will result in the cessation of study medication. Participants who discontinue medications will be expected to continue with study visits. Pregnancy test results and related outcome information will be collected on a Pregnancy and Outcome CRF. The site staff will follow the participant until an outcome of the pregnancy is known.

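### Two appendix sections attach an end of study visit to stopping treatment while other sections keep such participants in follow-up, so the week-24 viral load can be lost and an early draw has no stated status

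*Combined protocol and SAP*

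**What the plan says.** **Sections that attach an end of study visit to stopping treatment**

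- 23.9 describes voluntary withdrawal in terms of treatment: "A participant may also voluntarily withdraw from treatment due to what he/she perceives as an intolerable adverse event or for any other reason". It then says that on a request for voluntary withdrawal, or on removal from the study, "the participant will be asked to complete an end of study visit to assure safety and to document end of treatment outcomes".
- 24.2.5.3 concerns adverse events: "Individuals who experience an AE that compromises safe participation will be discontinued from further medication administration". It continues: "Study personnel will request that the participant complete an end of study visit to assure safety and to document end of treatment outcomes".

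**Sections that keep the participant in follow-up**

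- 9.6: "All participants will be followed for the duration of the study", with the exceptions "unless they withdraw consent, or the investigator or sponsor decides to discontinue their enrollment". Stopping medication is not among them.
- 24.2.5.4, the subsection directly after 24.2.5.3: "Participants who discontinue medications will be expected to continue with study visits".
- 12.9 explains being permanently finished with the study by death or withdrawal of consent. Stopping treatment is not mentioned.
- 12.8 provides a separate End of Treatment form for a permanent early treatment stop, and links the end of study visit to people who leave the trial early.

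**Link to the primary outcome**

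- 13.5 schedules HIV-1 RNA at screening, "12, and 24 weeks (or the end of study visit, if not week 24) for outcomes assessment".
- 17.2 defines suppression at 24 weeks from randomization and models months 3 and 6 only. Missing status is set to unsuppressed unless it lies between two suppressed values.

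**The concern.** The primary analysis is ITT at 24 weeks, so a participant who stops treatment but stays in the study should still contribute a week-24 viral load. Under 23.9 or 24.2.5.3 as worded, a site may hold an end of study visit when treatment stops and treat the participant as finished. The only late viral load would then be an early one.

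The plan does not say what happens to that value. If it is set aside, month 6 is missing and becomes unsuppressed, so stopping treatment is scored as a virologic failure. If it is used as month 6, suppression is scored at the wrong time. Either way the primary outcome depends on how a site reads the appendices, in an unblinded trial. A viral load that was never drawn may not be recoverable at analysis.

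**Working it through.** **1. The passages side by side**

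| Event | 23.9 / 24.2.5.3 | 9.6 / 12.9 / 24.2.5.4 |
|---|---|---|
| Voluntary withdrawal from treatment | End of study visit (23.9) | Not a listed reason to end follow-up (9.6, 12.9) |
| Medication stopped for an adverse event | End of study visit requested (24.2.5.3) | Not listed in 9.6 or 12.9 as such; visits continue (24.2.5.4, under Pregnancy) |
| Withdrawal of consent or termination from the study | End of study visit on removal (23.9) | Follow-up ends (9.6) |

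Only the last row is free of conflict. Appendix B disagrees with itself in adjacent subsections.

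**2. From an early visit to the primary outcome**

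- An early end of study visit replaces the week-24 draw (13.5).
- 17.2 and 17.10 do not say whether that draw is the month-6 value.
- If month 6 is missing, it becomes unsuppressed. The flanking exception gives no rescue from scheduled draws, because none follows week 24.
- Chart abstraction runs to 52 weeks and includes viral load (9.1.6), but its stated purpose is secondary outcomes. It does not clearly fill the gap.

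**3. The plan's power figure**

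Sections 17.1 and 17.7 give at least 80% power with 350 participants and an RR margin of 0.75, and about 480 for 90%. These come from bootstrapping 9 pilot participants whose visit-level data are not in the text reviewed, so they cannot be reproduced exactly. A simple approximation is

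Power = Φ( [ln(RR) − ln(0.75)] / SE − 1.96 ), with SE² = (1−p₁)/(n·p₁) + (1−p₀)/(n·p₀)

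where p₁ is XR-NTX, p₀ is TAU and n is the number per arm. With RR = 1 and n = 175 it gives 85.3% at 5/9 (pooled pilot, 17.7), 87.6% at 0.573 (17.6) and 80.0% at 0.52. At 0.52 and 480 participants it gives 90.7%. The rate 0.52 is back-solved, not stated in the plan.

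**4. Illustration of size**

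The documents give no rate of early end of study visits. Assume that:

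- true suppression is equal in both arms;
- a share w of the XR-NTX arm, and none of TAU, is truncated and recoded unsuppressed;
- those truncated would have been suppressed as often as the rest.

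Then p₁ = p₀(1−w) and the expected RR is 1−w. With p₀ = 0.57 and n = 175:

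- w = 0: SE² = 2 × 0.43/(175 × 0.57) = 0.00862, SE = 0.0929. Power = Φ(0.2877/0.0929 − 1.96) = 87%.
- w = 5%: p₁ = 0.5415, SE = 0.0957. Power = Φ((−0.0513 + 0.2877)/0.0957 − 1.96) = 70%.
- w = 10%: p₁ = 0.513, SE = 0.0987. Power = Φ((−0.1054 + 0.2877)/0.0987 − 1.96) = 46%.

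The range over two other common rates:

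| w (XR-NTX only) | Expected RR | Power, p₀ = 0.573 | Power, p₀ = 0.52 |
|---|---|---|---|
| 0 | 1.00 | 88% | 80% |
| 2.5% | 0.975 | 80% | 71% |
| 5% | 0.95 | 70% | 61% |
| 10% | 0.90 | 46% | 39% |
| 15% | 0.85 | 23% | 20% |

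Two variations soften this. If 10% were truncated in both arms, power would be 79% (0.573) or 71% (0.52). If those truncated would have been suppressed only 60% as often as the others, the expected RR is (1−w)/(1−0.4w), a loss of about 0.6w instead of w.

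**The case against.** The strongest reply is that the body of the protocol already shows the intent. Section 12.8 separates end of treatment from end of study, 12.9 names only death and consent withdrawal, and 9.6 does not list stopping medication. Section 23.9 is headed as withdrawal and pairs voluntary withdrawal with removal from the study. An adverse event that compromises safe participation could fall under the 9.6 exception that lets the investigator end enrollment. Section 24.2.5.4 sits under Pregnancy and may be meant narrowly. Neither appendix sentence expressly cancels later visits.

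Much of this stands. It shows which reading was probably intended, and a reader who infers that a site cannot comply with all these sections at once goes too far. It does not remove the conflict: 23.9 and 24.2.5.3 name treatment and medication, not enrollment, as the trigger for a visit that 12.8 ties to leaving the trial.

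Three other inferences are tempting and not supported:

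- **That only XR-NTX is affected.** Study medication and the hepatic stopping rule exist only in that arm, so the effect may fall more heavily there. But 7.4 counts TAU as a study intervention, 12.8 covers treatment received under TAU, and 23.9 speaks of treatment generally. No stop rates by arm are given.
- **That the documents imply a large w.** Multiplying the pilot's 42% initiation (4.3) by 47% non-retention (100% − 53%, from the placebo-controlled trial in 4.2) gives 0.42 × 0.47 = 20%. That counts all non-retention. Missed injections go through re-contact and rescheduling (9.2.3.3), initiation is allowed until week 20 (9.1.9), and participants already lost would lack week 24 under any rule. All 5 pilot OUD initiators were retained at 16 weeks, though that number is tiny.
- **That an early draw is analysed as week 24.** Section 13.5 governs collection. No section states a substitution rule.

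**Conclusion.** The concern holds as an internal inconsistency, at should-fix level. Following the appendix wording can cost the week-24 primary outcome of a participant who has only stopped treatment, and the plan leaves the status of an early viral load open.

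The size is unknown because no early-exit rate is given. The fall in power from about 87% to 70% (w = 5%) and 46% (w = 10%) rests on assumptions: truncation in XR-NTX only, recoding as unsuppressed, true RR of 1, a common rate of 0.57 and a simple two-proportion approximation in place of the planned GEE model. It shows sensitivity and does not forecast.

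Under those assumptions recoding works against a finding of non-inferiority, so the risk is lost power and an RR biased downward, not a false claim of non-inferiority. If early values were used as month 6, the direction is unknown.

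**What to change.** Reconcile the passages in line with 9.6 and 12.9.

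- **23.9 and 24.2.5.3:** keep the safety contact when treatment stops and complete the End of Treatment form (12.8). State that a participant who stops treatment without withdrawing consent or being terminated from the study continues all scheduled visits, including the week-12 and week-24 HIV-1 RNA. Reserve the end of study visit for leaving the study.
- **13.5 and 17.2:** state that an end-of-study HIV-1 RNA drawn before the week-24 window is not the week-24 outcome.

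The cost is wording in four sections. The form exists, and the visits and draws are already scheduled for every participant. No clinical rule for stopping treatment changes.
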